14.6.3. Efficacy

Derivations

WOMAC Osteoarthritis Index

- WOMAC questionnaire covers pain, stiffness and function related to osteoarthritis in the index knee. Participants will respond to each question using an 11-point NRS (0-10), with 0= **CCI** and 10= **CCI**
- For each of the subscales – pain, stiffness and function, the average of all the scores within that subscale will be calculated for each subject at each timepoint such that the average lies within the range of 0 to 10.
- The questions 1 to 5 constitute the subscale WOMAC pain, questions 6 and 7 constitute the subscale WOMAC stiffness, questions 8 to 24 constitute the subscale WOMAC function.
- If any of the scores within a subscale is missing for a participant, then the subscale will not be computed and will be set to missing for that participant.

Daily Pain NRS

- Average knee pain intensity: mean over the 7 days prior to each assessment visit
- Worst knee pain intensity: mean over the 7 days prior to each assessment visit

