8.3.3. WOMAC osteoarthritis index

[figure not shown]
WOMAC Index 3.1 will be completed by participants on paper questionnaires at time points specified in the SOA (Bellamy, 1988). The questionnaire covers pain, stiffness and function related to osteoarthritis in the index knee over the past 7 days. Participants will respond to each question using an 11-point NRS (0-10), with 0=no

They will be required to take at least 5 minutes to complete the questionnaire.

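### One blank item sets a whole WOMAC subscale to missing; on the single pre-dose form, that removes the participant from that exploratory subscale analysis

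*SAP*

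**What the plan says.** SAP 14.6.3 describes the scoring in three steps.

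- **Score.** For each subscale, "the average of all the scores within that subscale will be calculated for each subject at each timepoint", giving a value from 0 to 10.
- **Items.** "The questions 1 to 5 constitute the subscale WOMAC pain" (5 items), "questions 6 and 7 constitute the subscale WOMAC stiffness" (2 items) and "questions 8 to 24 constitute the subscale WOMAC function" (17 items).
- **Missing items.** "If any of the scores within a subscale is missing for a participant, then the subscale will not be computed"; the score is then set to missing.

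Protocol 8.3.3 adds that "WOMAC Index 3.1 will be completed by participants on paper questionnaires". Neither document gives a minimum number of answered items, a rule for averaging the answered ones, or a check of the paper form for blanks.

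SAP 7.2 places WOMAC among the exploratory efficacy analyses. SAP 7.2.5.1 fits a Bayesian repeated measures model to change from baseline at Weeks 1, 2, 4, 6 and 8, with baseline as a covariate. SAP 5.3 takes the latest non-missing pre-dose value as baseline and leaves baseline missing if there is none. The Part B schedule (Protocol 1.3.5, SAP 14.2.5) shows one pre-dose WOMAC, on Day 1.

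**The concern.** A mean can be computed from the items that were answered, so requiring all of them is a choice, and the SAP gives no reason for it. The same SAP is more tolerant where it matters more. For the co-primary pain scores, SAP 14.3 uses whatever diary days are available in a week, and SAP 5.3 accepts a baseline from 5 of 7 days (71%). A WOMAC function form with 16 of 17 items answered (94%) is rejected.

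At stake is information on function, stiffness and WOMAC pain in a Part B of about 50 participants. The effect depends on when the blank occurs. After baseline, it costs one visit's score, and the participant's other visits stay in the model. On Day 1 there is no earlier scheduled form to fall back on, so every change score for that subscale is lost.

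**Working it through.** **Inputs from the documents.** Item counts from SAP 14.6.3: pain 5 − 1 + 1 = 5; stiffness 7 − 6 + 1 = 2; function 24 − 8 + 1 = 17. Part B size of about 50, from Protocol 9.2.1. The plan states no figure on this point, so there is none to reproduce.

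**Answers discarded by one blank.** Function 17 − 1 = 16; pain 5 − 1 = 4; stiffness 2 − 1 = 1.

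**Assumed input.** The per-item blank rate p is not in the documents. I take 0.1% to 2% and treat blanks as independent across items and visits.

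**Loss per visit under the SAP rule.** P(subscale missing) = 1 − (1 − p)^k for k items. A function change from baseline needs a complete form on Day 1 and at the visit: 1 − (1 − p)^34.

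| p (assumed) | Pain, k = 5 | Stiffness, k = 2 | Function, k = 17 | Function scores lost, of 50 | Function change score lost at a given visit |
|---|---|---|---|---|---|
| 0.1% | 0.5% | 0.2% | 1.7% | 0.8 | 3.3% |
| 0.5% | 2.5% | 1.0% | 8.2% | 4.1 | 15.7% |
| 1% | 4.9% | 2.0% | 15.7% | 7.9 | 28.9% |
| 2% | 9.6% | 4.0% | 29.1% | 14.5 | 49.7% |

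The single-visit function column is also the probability that the Day 1 form fails. Applied to Day 1, the of-50 column is therefore the expected number of participants who drop out of the function analysis altogether.

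**Loss under an illustrative minimum.** With 14 of 17 function items required, a score is lost only with four or more blanks. At p = 2% the leading term is C(17,4) × 0.02⁴ × 0.98¹³ = 0.00029, and the total is about 0.03%. With 4 of 5 pain items required, the loss at 2% is 1 − 0.98⁵ − 5 × 0.02 × 0.98⁴ = 0.004, or 0.4%.

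**Error from averaging the answered items.** With one function item blank, the full mean differs from the mean of the other 16 by (blank item − mean of the other 16)/17. That is at most 10/17 = 0.59 points, and 2/17 = 0.12 if the item differs from the rest by 2 points. With three function items blank, each 2 points from the mean of the rest, the error is 3 × 2/17 = 0.35. One blank pain item 2 points from the rest gives 2/5 = 0.40. These are errors in one participant's score, not in the treatment difference.

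**The case against.** The rule is explicit, pre-specified, identical in both arms and contradicts nothing else in the plan. Complete-item scoring is a legitimate convention, and no minimum-item threshold can be drawn from the documents. This stands: the point is about efficiency, not an error, and the threshold below is a proposed convention.

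The size of the loss is assumed. A reader might infer that blanks are likely because the form is on paper. The documents do not support that: they give no rate, the form is completed at clinic visits before other assessments, and Protocol 8.3.3 asks participants to take at least 5 minutes. A completeness check could sit in the Study Reference Manual, which is not available here. A skipped page or one habitually skipped item would also cluster the blanks and lower the loss at the same average rate. This stands too.

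A missing-score rate is not a loss of precision. The repeated measures model keeps the participant's other visits and partly recovers a missed post-baseline score. That is right after baseline, but it gives no help when the Day 1 score is missing.

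Averaging the answered items may introduce bias. Someone who leaves an item blank because they no longer do the activity may have worse function than the answered items show, and change scores could mix different items at baseline and at the visit. This is a fair limit on the remedy and the reason to keep the present rule as a sensitivity analysis.

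Two stronger readings are tempting. One is that the rule weakens the trial's main efficacy conclusion. It does not: the co-primary endpoints, the decision criteria in Protocol 9.2.1 and the sample size re-estimation in SAP 7.1.5.1 rest on the daily diary pain scores. The other is that one blank at any visit deletes the subscale at every visit, because the missing-item sentence names the participant and not the timepoint. The scoring rule in the same list works per timepoint, so the per-visit reading is the natural one, though the SAP should say so.

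**Conclusion.** The point holds as a minor, inexpensive improvement to an exploratory analysis. The certain part is structural: one blank discards 16 function answers, and one blank function item on Day 1 removes the participant from the function analysis at all five weeks, unless an unscheduled pre-dose form exists. The amount lost is not known. Under independent blanks it runs from 1.7% of function scores per visit at an assumed 0.1% item-blank rate to 29.1% at 2%, with clustering pulling it down. The loss of precision in the treatment difference was not calculated and would be less than these rates suggest for post-baseline visits.

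**What to change.** Before the final unblinding, amend SAP 14.6.3 as follows.

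- At each timepoint, compute the subscale as the mean of the answered items when a stated minimum is answered, for example 4 of 5 for pain, 14 of 17 for function and both items for stiffness. Below that, set it to missing at that timepoint only.
- Keep the complete-item rule as a sensitivity analysis.
- Report the number of blank items by visit and arm, so that the actual loss is visible.

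If forms are still being collected, a site check for blanks at the visit, above all on Day 1, would prevent much of the problem.

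The cost is one SAP sentence, a small derivation change and one extra run of the model. The price in assumptions is that a blank item resembles the answered ones, which may fail for activities a participant no longer does; the sensitivity analysis shows whether that matters.

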14.6.4. Safety

ECG Parameters	
RR Interval	

 IF RR interval (msec) is not provided directly, then RR can be derived as: 
 [1] If QTcB is machine read & QTcF is not provided, then : $RR = \left[\left(\frac{QT}{QTcB} \right)^2 \right] * 1000$ 	

 [2] If QTcF is machine read and QTcB is not provided, then: $RR = \left[\left(\frac{QT}{QTcF} \right)^3 \right] * 1000$	

 if both the QTcB and QTcF values are machine read and provided, RR will not be calculated. If ECGs are manually read, the RR value preceding the measurement QT interval should be a collected value, THEN do not derive. 	
Corrected QT Intervals	

 When not entered directly in the eCRF, corrected QT intervals by Bazett's (QTcB) and Fredericia's (QTcF) formulas will be calculated, in msec, depending on the availability of other measurements. IF RR interval (msec) is provided then missing QTcB and/or QTcF will be derived as: 	
$QTcB = \frac{QT}{\sqrt{\frac{RR}{1000}}}$ $QTcF = \frac{QT}{\sqrt[3]{\frac{RR}{1000}}}$	
Worst Case Rules	

Worst case finding based on the interpretation and the clinical significance:
 
 Count the subject as 'ABNORMAL' and 'CLINICALLY SIGNIFICANT', if any of the findings are 'ABNORMAL' and 'CLINICALLY SIGNIFICANT' during the time period/Post-Baseline. Else count the subject as 'ABNORMAL' and 'NOT CLINICALLY SIGNIFICANT', if any of the findings are 'ABNORMAL' and 'NOT CLINICALLY SIGNIFICANT' and none of the findings are 'ABNORMAL' and 'CLINICALLY SIGNIFICANT' during the time period/Post-Baseline. Else count the subject as 'NORMAL' if there is a finding of 'NORMAL' and none of the findings are 'ABNORMAL' during the time period/Post-Baseline. Otherwise, do not count the subject during the time period/Post-Baseline, i.e. little n will reflect that the subject is not counted in the time period/Post-Baseline.. 	

Laboratory Parameters	

 All BLQ values will be imputed with $\frac{1}{2}$ LLOQ. All ALQ values will be imputed with the ALQ + [smallest positive number with the same number of decimal places as the ALQ is reported with] Values reported as $< x$ are assumed to have an LLOQ of x. Values reported as $> x$ are assumed to have an ALQ of x. 	

14.6.5. Immunogenicity

A seed (5315) will be generated using code as outlined in Section [14.9.2](#). This will be saved in the refdata area.

- Using the generated seed, random numbers will be generated for all subjects that exist in the imgen dataset.
- These subjects will be ordered based on the random number and letters assigned sequentially (i.e. the patient with the smallest random number was ‘a’, the next patient ‘b’ and so on).

14.7. Appendix 7: Reporting Standards for Missing Data

14.7.1. Premature Withdrawals

Element	Reporting Detail
General	
 • A participant is considered to have completed the study if he/she has completed all phases of the study including the final follow-up visit • All available data from participants who were withdrawn from the study will be listed and all available planned data will be included in summary tables and figures, unless otherwise specified.

14.7.2. Handling of Missing Data

Element	Reporting Detail
General	
 • Missing data occurs when any requested data is not provided, leading to blank fields on the collection instrument: 
 ○ These data will be indicated by the use of a “blank” in participant listing displays. Unless all data for a specific visit are missing in which case the data is excluded from the table. ○ Answers such as “Not applicable” and “Not evaluable” are not considered to be missing data and should be displayed as such.

14.7.2.1. Handling of Missing and Partial Dates

Element	Reporting Detail		
General	
 • Partial dates will be displayed as captured in participant listing displays. • Where necessary, display macros may impute dates as temporary variables for sorting data in listings only. In addition, partial dates may be imputed for ‘slotting’ data to study or for specific analysis purposes. 		
Adverse Events	
 • Imputations in the adverse events dataset are used for slotting events to the appropriate study time periods and for sorting in data listings. • Partial dates for AE recorded in the CRF will be imputed using the following conventions: 
 
 Missing start day	 
 • If study treatment start date is missing (i.e. participant did not start study treatment), then set start date = 1st of month. • Else if study treatment start date is not missing: 
 ○ If month and year of start date = month and year of study treatment start date then 
 ▪ If stop date contains a full date and stop date is earlier than study treatment start date then set start date= 1st of month. ▪ Else set start date = study treatment start date. ○ Else set start date = 1st of month. 	
 
 	Missing start day	
 • If study treatment start date is missing (i.e. participant did not start study treatment), then set start date = 1st of month. • Else if study treatment start date is not missing: 
 ○ If month and year of start date = month and year of study treatment start date then 
 ▪ If stop date contains a full date and stop date is earlier than study treatment start date then set start date= 1st of month. ▪ Else set start date = study treatment start date. ○ Else set start date = 1st of month.
Missing start day	
 • If study treatment start date is missing (i.e. participant did not start study treatment), then set start date = 1st of month. • Else if study treatment start date is not missing: 
 ○ If month and year of start date = month and year of study treatment start date then 
 ▪ If stop date contains a full date and stop date is earlier than study treatment start date then set start date= 1st of month. ▪ Else set start date = study treatment start date. ○ Else set start date = 1st of month. 		

Element	Reporting Detail		
	Missing start day and month	
 • If study treatment start date is missing (i.e. participant did not start study treatment), then set start date = January 1. • Else if study treatment start date is not missing: 
 ◦ If year of start date = year of study treatment start date then 
 ▪ If stop date contains a full date and stop date is earlier than study treatment start date then set start date = January 1. ▪ Else set start date = study treatment start date. ◦ Else set start date = January 1. 	
	Missing stop day	Last day of the month will be used.	
	Missing stop day and month	No Imputation	
	Completely missing start/end date	No imputation	
Concomitant Medications	
 • Partial dates for any concomitant medications recorded in the CRF will be imputed using the following convention: 	Missing start day	
 • If study treatment start date is missing (i.e. participant did not start study treatment), then set start date = 1st of month. • Else if study treatment start date is not missing: 
 ◦ If month and year of start date = month and year of study treatment start date then 
 ▪ If stop date contains a full date and stop date is earlier than study treatment start date then set start date= 1st of month. ▪ Else set start date = study treatment start date. ◦ Else set start date = 1st of month.
		Missing start day and month	
 • If study treatment start date is missing (i.e. participant did not start study treatment), then set start date = January 1. • Else if study treatment start date is not missing: 
 ◦ If year of start date = year of study treatment start date then 
 ▪ If stop date contains a full date and stop date is earlier than study treatment start date then set start date = January 1. ▪ Else set start date = study treatment start date. ◦ Else set start date = January 1.
		Missing end day	A '28/29/30/31' will be used for the day (dependent on the month and year)

Element	Reporting Detail	
	Missing end day and month	A '31' will be used for the day and 'Dec' will be used for the month.
	Completely missing start/end date	No imputation
		
• The recorded partial date will be displayed in listings.

14.8. Appendix 8: Values of Potential Clinical Importance

14.8.1. PCI Values for Part A

14.8.1.1. Vital Signs

Vital Sign Parameter (Absolute)	Units	Clinical Concern Range	
		Lower	Upper
Systolic Blood Pressure	mmHg	< 85	> 160
Diastolic Blood Pressure	mmHg	< 45	> 100
Heart Rate	Bpm	< 40	> 110

14.8.1.2. Laboratory Values

Haematology				
Laboratory Parameter	Units	Category	Clinical Concern Range	
			Low Flag (< x)	High Flag (>x)
Hematocrit	Ratio of 1	Male	0.39	0.54
		Female	0.35	0.49
		Δ from BL	↓0.075	
Hemoglobin	g/L	Male	124	180
		Female	109	180
		Δ from BL	↓25	
Lymphocytes	x10 ⁹ / L		0.75	
Neutrophil Count	x10 ⁹ / L		1.5	
Platelet Count	x10 ⁹ / L		100	550
White Blood Cell Count (WBC)	x10 ⁹ / L		2.5	20

Clinical Chemistry				
Laboratory Parameter	Units	Category	Clinical Concern Range	
			Low Flag (< x)	High Flag (>x)
Albumin	g/L		30	
Calcium	mmol/L		2	2.75
Creatinine	umol/L			1.3 X ULN
Creatinine	umol/L	Δ from BL		↑ 44.2
Glucose	mmol/L		3	9
Potassium	mmol/L		3	5.5
Sodium	mmol/L		130	150
Total CO ₂	mmol/L		18	32
Creatinine Kinase	mg/dL			>1.6 X ULN
C-reactive Protein	mg/L			≥3.0
Troponin T	ng/L			14.1

Liver Function			
Test Analyte	Units	Category	Clinical Concern Range
ALT/SGPT	IU/L	High	≥2xULN
AST/SGOT	IU/L	High	≥2xULN
AlkPhos	IU/L	High	≥2xULN
T Bilirubin	µmol/L	High	≥1.5xULN
T. Bilirubin + ALT	µmol/L IU/L	High	ALT≥3xULN AND bilirubin≥ 1.5xULN

14.8.1.3. ECG

ECG Parameter	Units	Clinical Concern Range	
		Lower	Upper
Absolute			
Absolute QTc Interval	msec		>500
Absolute PR Interval	msec	<110	>220
Absolute QRS Interval	msec	<75	>120
Change from Baseline			
Increase from Baseline QTc	msec		>60

14.8.2. PCI Values for Part B

14.8.2.1. Vital Signs

Vital Sign Parameter (Absolute)	Units	Clinical Concern Range	
		Lower	Upper
Systolic Blood Pressure	mmHg	< 85	> 160
Diastolic Blood Pressure	mmHg	< 45	> 100
Heart Rate	bpm	< 40	> 110

14.8.2.2. Laboratory Values

Haematology				
Laboratory Parameter	Units	Category	Clinical Concern Range	
			Low Flag (< x)	High Flag (>x)
Hematocrit	Ratio of 1	Male	0.39	0.54
		Female	0.35	0.49
		Δ from BL	↓0.075	
Hemoglobin	g/L	Male	124	180
		Female	109	180
		Δ from BL	↓25	
Lymphocytes	x10 ⁹ / L		0.75	4.5
Neutrophil Count	x10 ⁹ / L		1.5	8.0
Platelet Count	x10 ⁹ / L		100	550
White Blood Cell Count (WBC)	x10 ⁹ / L		2.5	15

Haematology				
Laboratory Parameter	Units	Category	Clinical Concern Range	
			Low Flag (< x)	High Flag (>x)
Clinical Chemistry				
Laboratory Parameter	Units	Category	Clinical Concern Range	
			Low Flag (< x)	High Flag (>x)
Calcium	mmol/L		2	2.60
Creatinine	umol/L	Male		120
		Female		100
Creatinine	umol/L	Δ from BL		↑ 44.2
Glucose	mmol/L		3	8
Potassium	mmol/L		3	5.5
Sodium	mmol/L		130	150
Troponin T	ng/L			14.1
NT-pro BNP	ng/L			125.2

Liver Function				
Test Analyte	Units	Category	Clinical Concern Range	
ALT/SGPT	IU/L	High	≥1.5xULN	
AST/SGOT	IU/L	High	≥1.5xULN	
AlkPhos	IU/L	High	≥1.5xULN	
T Bilirubin	μmol/L	High	≥1.5xULN	
T. Bilirubin + ALT	μmol/L IU/L	High	ALT≥3xULN AND bilirubin≥ 1.5xULN	

Immunology				
Test Analyte	Units	Category	Clinical Concern Range	
			Low Flag (< x)	High Flag (>x)
Complement C3	g/L	High	0.85	1.8
Complement C4	g/L	High	0.1	0.4

Virology				
Test Analyte	Units	Category	Clinical Concern Range	
Hepatitis C Antibody	N/A	High	Reactive	

14.8.2.3. ECG

ECG Parameter	Units	Clinical Concern Range	
		Lower	Upper
Absolute			
Absolute QTc Interval	msec	<350	>450
Absolute PR Interval	msec	<110	>220
Absolute QRS Interval	msec	<75	>120
Change from Baseline			
Increase from Baseline QTc	msec		>50

14.9. Appendix 9: Statistical Algorithms and Model Checking

14.9.1. Calculation of SD from Bayesian Repeated Measures model

1. Calculate the R Correlation matrix (correlation matrix for the repeated measures [in this case visit])

$$R_{corr} = \begin{bmatrix} 1 & \rho_{1,2} & \cdots & \rho_{1,8} \\ & 1 & \cdots & \rho_{2,8} \\ & & \cdots & \cdots \\ & & & 1 \end{bmatrix}$$

2. Calculate the number of subject contributing data up to each week (e.g. 32 subjects have up to week 8, a further 4 subjects contribute up to week 6 only, 3 more contribute data up to week 4 only.

$$\mathbf{n}_{cont} = \begin{bmatrix} n_{1,8} \\ n_{2,8} \\ \cdots \\ n_{7,8} \end{bmatrix} = \begin{bmatrix} n_1 \\ n_2 \\ \cdots \\ n_7 \end{bmatrix} - \begin{bmatrix} n_8 \\ n_8 \\ \cdots \\ n_8 \end{bmatrix}$$

$$ESS_8 = n_8 + \sum_{i=1, \dots, 7} \rho_{i,8} n_{i,8}$$

3. Calculate the SD

$$SD_{estimate,8} = SE_8 * \sqrt{ESS_8}$$

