7.1.5. Statistical Analyses / Methods

7.1.5.1. Statistical Methodology Specification

Endpoint / Variables

 • Change from baseline in Average Knee Pain Intensity at Week 8 • Change from baseline in Worst Knee Pain Intensity at Week 8
Model Specification

 • A Bayesian repeated measures model will be used to fit the change from baseline from Week 1 to Week 8. • The endpoints will be assumed to follow a multivariate (MVN) normal distribution to model all repeated measurements within the same participant. • Markov-Chain-Monte-Carlo (MCMC) method will be used to estimate the posterior distributions. • A linear model for Change from Baseline at each Week (visit) will be constructed to model the within-participant covariance structures. • Terms fitted in the model will include: 
 ○ Categorical: Week (Week 1 to Week 8), Treatment (GSK3858279 and placebo), Treatment*Week Interaction, Baseline*Week Interaction ○ Continuous: Baseline ○ Repeated: Week • The prior for the Variance Covariance Matrix will follow an Inverse Wishart Distribution. • Vague priors (normal (0, var=1e6)) will be used for all other model parameters. • Set simulation size at a minimum of 10000 and 1000 burn-in iterations. The simulation size and number of burn-in iterations could be updated during the convergence check. • Refer to Appendix 6 - Bayesian Repeated Measures Model (PROC MCMC) for additional information • Refer to Appendix 3 for details on visit computation. • Refer to Appendix 9 for additional information
Model Checking & Diagnostics

 ○ Bayesian Analyses: Refer to the relevant documentation (Bayesian Statistics Best Practice at GSK – Clinical Trials using Bayesian Inference). • Refer to Appendix 9
Model Results Presentation

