
 • Medians and 95% credible intervals will be produced by treatment group and for the difference between treatment groups, for each of the endpoints, • The posterior distributions will be used to produce several probability statements: 
 ○ $P[True\ Difference\ (GSK3858279 - placebo) < X]$ ○ where values of X to be generated are 0, -0.6, -0.8 and -1.0 • For all tables/figures presenting results from a statistical model, a footnote including model, prior distributions, covariates and a very brief mention of intercurrent events will be added. • For all TFLs presenting efficacy endpoints, a footnote to state a range of the score for the endpoint specifying which direction of change is an improvement.

Interim Analysis 1

- A first interim analysis will occur once 20 participants reach Week 4
- The endpoint will be Change from baseline in average knee pain intensity at week 4

Interim Analysis 2

- A second interim analysis may occur once approximately 45 participants have been randomised (this estimated to happen when 28 participants reach Week 8) and will include a sample size re-estimation and a futility assessment. In addition to posterior probabilities, predictive probabilities of achieving criteria of interest at the end of the study will be estimated using a Bayesian Normal-Normal update. Vague priors for all modelling parameters will be used to compute the posterior distributions.
- Criteria of interest are:
 - $P[\text{True Difference (GSK3858279} - \text{placebo}) < X]$ where values of X to be generated are 0, -0.6, -0.8 and -1.0 and
 - Predictive probability $> X\%$
- At the interim analysis an estimate of the standard deviation of the endpoint at week 8 will be estimated from the Bayesian Repeated Measures model. Details are given in Section 14.9.1. All data available at the time of the interim will be used for this purpose
- The ratio of the Estimated SD to Predicted SD (SD=1.8) for the change from baseline at Week 8 will be used to calculate the optimal sample size as follows:

$$SS_{optimal} = \left(\frac{SD_{estimated}}{1.8} \times \sqrt{50} \right)^2$$

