- The optimal sample size must be within the range [# participants randomised, 80] subjects (i.e. if the optimal calculation is >80, the SS will be capped at 80/ if the optimal calculation is <50, the SS will be capped at # participants randomised). The number of participants resulting from the SS_optimal formula must be rounded up to the next even number.

Subgroup Analyses

- No subgroup analysis is planned for the study.

Sensitivity Analyses

- Refer to Section 14.9.2 for additional information.

Supportive Analyses

- The Bayesian Repeated Measures Model will be performed on the Per Protocol Population if the Per Protocol Population comprises 50 to 90% of the ITT population

CCI

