14.9.2. Model Checking & Diagnostics

Bayesian Repeated Measures Model

Seeds for all planned analyses will be determined using the following SAS code

```
data temp;
do i=1 to #seed;
  number=round(10000*ranuni(207804),1); output;
end;
run;
```

The following points are for guidance and illustration and do not guarantee a successful model convergence. They cannot cover all eventualities and do not remove the requirement to do what is best for the specific set of observed data being modelled.

Priors

Unless otherwise specified the following would be the default approach to selecting prior distributions:

- Vague priors of the form $Normal(0, Var=1E6)$ would be assigned to each fixed effect in the proposed statistical model.

- Vague Inverse-gamma priors of the form $\text{IGamma}(0.001, 0.001)$ would be assigned to stand-alone variance parameters that are not expected to take values near zero (e.g. for the residual variance rather than a random effect variance component)
- For stand-alone variance parameters that may take values close to zero a noninformative prior of the form $\text{Uniform}(0, XXX)$ may be assigned for the SD
- For repeated measures models Inverse-Wishart priors will be assigned for the Variance Covariance matrix (VCV). They would use degrees of freedom equal to the dimension of the VCV matrix and an Identity matrix (of the same dimension).
 - If there are issues with those variance parameters then the Identity matrix may be replaced with a diagonal matrix that uses best guesses for the residual variance at each repeated measure time point (or the residual estimates from fitting simple models).
 - It is good practice to ensure that each prior distribution is visualised to ensure it appears sensible and allows clinically plausible response values, whilst not allowing impossible values to be drawn with high probability and that if it is intended to be non-informative it is doing so over the region of the likelihood function.

Checking convergence and other diagnostics

The key model diagnostic output is the MCSE/SD ratio for each parameter:

- Adequate values for the number of MCMC samples / thinning / number of burn in samples should be chosen to ensure that the MCSE/SD for the key parameters is below 0.01 (e.g. key parameters those associated with treatment, or as pre-specified comparisons of interest) in each final model.

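### The Week 8 SD formula for the sample-size re-estimation (SAP 14.9.1) contradicts its own example and leaves SE_8 undefined; followed as printed, it would generally overstate the SD and N

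*SAP*

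**What the plan says.** SAP 7.1.5.1 places an optional second interim analysis "once approximately 45 participants have been randomised (this estimated to happen when 28 participants reach Week 8". The Week 8 SD is estimated from the Bayesian repeated measures model and enters N = 50 × (SD/1.8)². N is rounded up to an even number and kept between the number randomised and 80: "if the optimal calculation is >80, the SS will be capped at 80". For the SD the reader is sent on: "Details are given in Section 14.9.1. All data available at the time of the interim will be used for this purpose".

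SAP 14.9.1 then gives three steps.

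1. Obtain the correlation matrix across weeks.
2. "Calculate the number of subject contributing data up to each week", with the example of 32 participants to Week 8, "a further 4 subjects contribute up to week 6 only, 3 more contribute data up to week 4 only". The printed equations are n_{i,8} = n_i − n_8 for i = 1 to 7, and ESS_8 = n_8 + Σ ρ_{i,8} n_{i,8}.
3. SD = SE_8 × √ESS_8.

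Step 3 is the only place where SE_8 appears. n_i is not defined separately either. The outputs listed for the model in 7.1.5.1 are: "Medians and 95% credible intervals will be produced by treatment group and for the difference between treatment groups".

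**The concern.** There are two separate defects.

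- **Counting.** The words and the example sort people by their last week, so each appears once. The formula subtracts n_8 from the count at every week and adds up all seven differences. With n_i as the number with data at week i, someone last seen at week k enters k times. With positive correlations this inflates ESS_8, and so the SD, even when SE_8 is on the right basis.
- **SE_8.** The text does not say whether it belongs to an arm mean, the treatment difference or a pooled mean, or whether the counts are per arm or total. The example counts are not split by arm.

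N depends on SD squared, so any relative error in ESS_8 or in SE_8² passes in full to N. Partial follow-up is also the expected situation: 45 randomised with 28 at Week 8 leaves 45 − 28 = 17 people with incomplete data, and the plan uses all of it.

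**Working it through.** **Anchor.** Protocol 9.2.1 uses 25 per arm and SD 1.8. The SE of the difference is 1.8 × √(2/25) = 0.509, and 1/0.509 = 1.964. The positive rate at a true difference of 1 is Φ(1.964 − 1.282) = 75.3% (stated 75%). The negative rate at 0 is Φ(1.964 − 1.036) = 82.3% (stated 82%). The re-estimation formula returns 50 at SD 1.8, so 50 is the correct answer in what follows.

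**SAP example, printed formula.** For weeks 1 to 7, n_i = 39, 39, 39, 39, 36, 36, 32, with n_8 = 32. The differences are 7, 7, 7, 7, 4, 4, 0, which sum to 36 entries for 7 people. At constant ρ = 0.5 (an assumption), ESS_8 = 32 + 0.5 × 36 = 50.0. An effective sample size cannot exceed the 39 people, yet this one does once ρ passes 7/36 = 0.19.

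**SAP example, exact.** With a free mean per week, known covariance and monotone dropout, the variance of the Week 8 mean divided by σ² is (1 − R²₆)/32 + (R²₆ − R²₄)/36 + R²₄/39. Here R²_k = kρ²/(1 + (k − 1)ρ) is the share of Week 8 variance explained by weeks 1 to k. At ρ = 0.5, R²₄ = 0.400 and R²₆ = 0.429. The sum is 0.01786 + 0.00079 + 0.01026 = 0.02891, so the exact ESS is 34.6.

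**Result.** SD = 1.8 × √(50.0/34.6) = 2.16 and N = 50 × 50.0/34.6 = 72.3. Counting each person once, still ρ-weighted, gives ESS 32 + 0.5 × 7 = 35.5 and N = 51.3. Most of the excess therefore comes from repeated counting.

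**Range.** The documents give neither correlations nor the spread of follow-up. The assumed range is constant ρ 0.2 to 0.8 and AR(1) 0.5 to 0.9. True SD is 1.8, SE_8 is on the same basis as the counts, and N is shown before the cap.

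| Follow-up pattern | N, printed formula | N, each person once |
|---|---|---|
| SAP example, 32/4/3 | 53–82 | 51–53 |
| 28 of 45 at Week 8, other 17 spread evenly over weeks 1–7 | 57–106 | 53–57 |
| 28 of 45, other 17 last seen at weeks 1–3 (6/6/5) | 51–72 | 51–59 |
| 40 of 45 at Week 8, other 5 spread evenly | 51–64 | 51 |

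The smallest effect is N = 50.8, for early-only partial data at AR(1) 0.5.

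**SE_8 alone, complete data, counts pooled over two equal arms.** The SE of one arm mean is √2 times the pooled SE, and that of the difference is 2 times.

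- One arm: SD = 1.8 × √2 = 2.55, N = 50 × 2 = 100. The cap is reached from a true SD of 1.8 × √(80/100) = 1.61.
- Difference: SD = 1.8 × 2 = 3.60, N = 50 × 4 = 200. The cap is reached from 1.8 × √(80/200) = 1.14.

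Protocol 9.2.2 considers SDs of 1.4, 1.8, 2, 2.2 and 2.4. The difference reading hits the cap at all five, the one-arm reading at all but 1.4.

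**Supporting simulation.** The SAP model was simulated with the inverse-Wishart prior of 14.9.2, flat fixed effects in place of variance 1e6, residual SD 1.8 and 200 trials per scenario. Scenarios were AR(1) 0.8 and constant 0.5, each with the even 28-of-45 and the SAP-example pattern. The square root of the (8,8) covariance element had mean 1.79 to 1.83 and gave median N 48 to 50. The printed formula with a pooled SE had mean SD 2.09 to 2.45 and median N 68 to 91.

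**The case against.** n_i is not defined, so repeated counting is an inference from its natural reading. If n_i meant n_8 plus those whose last week is exactly i, formula and example would agree. The SAP does not say this, and the other literal reading (only those whose last week is i) gives negative counts: 4 − 32 = −28 and 3 − 32 = −29. The natural reading is the one a programmer would most likely code.

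The direction is not certain either. A pooled-mean SE with per-arm counts would understate the SD (1.8/√2 = 1.27, N = 25, raised to the number randomised). But 7.1.5.1 reports no pooled mean, and the case only underlines that SE_8 needs a definition. The counting and SE_8 sizes above are also separate scenarios, not to be added together.

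The Interim Analysis Charter or the separate output shells, neither available here, may define both symbols. That stands as a limit: the point concerns what the SAP prints, not what was run. The SAP does, however, name 14.9.1 as the place for the details.

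The harm is bounded, and that also stands. The interim is optional, N cannot exceed the protocol's own maximum of 80, and the final posterior does not use this SD.

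**Conclusion.** The concern holds. The formula in 14.9.1 does not match its example, can return an effective sample size larger than the number of people, and rests on an undefined SE_8. Confidence in these points is high.

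The size is conditional. With SE_8 on the same basis as the counts and positive correlations, N would come out between about 51 (negligible) and above the cap when 50 is right. With an arm or difference SE and pooled counts, the re-estimation would sit at 80 for most of the SDs the protocol considers. What is at stake is up to 80 − 50 = 30 unnecessary participants and a wrong SD in the re-estimation table (SAP 14.11.5). The final efficacy inference is not biased by this SD. It should be fixed.

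**What to change.** Drop the ESS step. Define the Week 8 SD as the square root of the posterior median of the (8,8) element of the residual variance-covariance matrix. The model already estimates that matrix: "The prior for the Variance Covariance Matrix will follow an Inverse Wishart Distribution". This needs neither ESS_8 nor SE_8, and it uses partial follow-up through the likelihood.

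If an ESS is kept, it would have to count each participant once by last observed week, state the basis of SE_8 and of the counts, say how the two arms are combined into one SD, and label the result approximate. Week-to-week differences of n_i are not a safe substitute: if one of the 32 completers had no Week 7 diary data, n_7 − n_8 would be −1.

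The SAP version history shows outputs already added for a fourth interim analysis, so the second may be past. If so, check which counts and which SE_8 the executed code used, recompute the SD from the covariance matrix, and report both.

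The cost is wording in the SAP and the Interim Analysis Charter and one line of code. No extra data are needed.
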